## 8.2 Main trial outcomes

### 8.2.1 Primary outcome(s)

Primary outcome is complications experienced post-op until discharge measured using the CCI at discharge from hospital.

#### Comprehensive Complication Index

The CCI is based on the conventional CDC which has been widely used in surgical research[36, 37]. The CCI is the mathematical summation of complications graded using the conventional CDC and takes into account the number and severity of each complication to obtain a value from 0 (no complications) to 100 (death). As all post-operative complications are included it is more sensitive than other surgical morbidity endpoints[38]. There is an online tool available to calculate the CCI at [CCICalculator.com](http://CCICalculator.com).

### 8.2.2 Secondary outcomes

#### 8.2.2.1 Clinical (timepoints relative to Index operation)

- Number and severity of complications at 30 and 90 days post-operation, assessed using the CCI[29].
- Number of complications (respiratory, cardiovascular, SSI, reoperation), including mortality, recorded by clinical team during inpatient stay, and reported by the participant at 30 and 90 days post-operation, collected through hospital records and measured using the CDC system[36].
- Number of infectious complications (SSI, vascular access line infection, hospital acquired pneumonia, urinary tract infection, all defined according to the CDC definitions[39]) assessed in hospital, prior to discharge.
- Barthel index of function (including activities of daily living)[40], completed by the clinical team / site staff at discharge, 30 and 90 days post-operation.
- Sit to stand test[41], at point of discharge.

## TONIC: Protocol

---

- Quality of recovery (QoR-15), to measure quality of recovery after surgery and analgesia, participant completed at discharge, 30 and 90 days[42] post-operation.
- Length of post-operative hospital stay from operation to day of discharge (in nights following operation), collected through hospital records.
- Unplanned hospital readmission at 30 and 90 days following discharge up to 90 days post-operation, collected through hospital records.
- Discharge destination (usual residence, residential, or nursing home), collected through hospital records.
- EuroQol-5D-5L[43] (EQ-5D-5L) Health status questionnaire used to derive quality adjusted life years (QALYs), quality of life, and is used in the cost effectiveness analysis, participant completed, at discharge, 30, and 90 days post-operation.
- Patient reported outcome measure of gastrointestinal recovery (PRO-diGI) at discharge, 30, and 90 days post-operation. Includes domains related to pain, nausea, and psychological wellbeing [44].
- Assessment of patient treatment satisfaction using a 0-100 visual analogue scale, patient completed at 30 and 90 days post-operation.
- Use and duration of PN, and total calories administered post-operatively, will be recorded for each arm at discharge.
- Use of other nutritional interventions (oral nutritional supplements) prior to discharge, will also be recorded for each arm.
- Process metrics: time from randomisation to line insertion, and time from operation to starting PN in hours.

### 8.2.2.2 Economic

- Incremental cost per QALY at 90 days post-operation from an NHS and societal cost perspective.
- Incremental cost per QALY over lifetime horizon from an NHS cost perspective.
- Expected Value of Perfect Information analysis over lifetime horizon.

## 9. TRIAL PROCEDURES

### Screening

Potential participants will be identified by the clinical team and the study introduced. With their permission, potential participant's information will be passed to the research team. Once the patient has been identified they will be entered on the screening log. The clinical team will ensure the patient meets the eligibility criteria. If the patient meets the eligibility criteria, the identifying clinical team member will provide the PIS to the patient. If the patient lacks capacity, the trial will be briefly discussed with them, and they will be given the Summary PIS and the trial will be discussed with the patient's relative or carer (Personal Consultee or Legal Representative).

### Consent

If the identifying doctors/nurse/research team member are on the Site Signature and Delegation Log and have been delegated the task of taking consent, consent can be taken by them. If they are not on the delegation log as able to take consent, consent should be taken by a member of the site research team delegated this task.

Consent should be obtained from the patient, unless the patient lacks capacity, in which case, consent should be obtained from the patient's relative or carer (Personal Consultee or Legal Representative).

### Baseline (Pre-randomisation)

Once informed consent has been obtained, patients will have key demographic data recorded. The research team will enter the data items needed to determine the Nutrition Risk Screening (NRS-2002) score on to the online EDC system, which will then calculate the score. Data collected as part of routine care includes the MUST, medical history, and the NELA mortality risk score. The patient will also complete an EQ-5D-5L questionnaire. The participant is to be guided to complete the questions on the EQ-5D-5L based on their health and wellbeing prior to the start of the episode that requires surgery. If the participant is not able to complete this then EQ-5D-5L will not be recorded.

### Randomisation

Once consented and baseline assessments are completed, the patient can be randomised into the TONIC Trial. Details of both date and time of randomisation along with the randomised allocation will be recorded by the EDC system.

## **Interventions**

Participants will be randomised to receive early PN (Intervention) or standard care. The intervention arm is the intervention plus standard care. See section 7 for full information on the trial interventions.

### **Intraoperative**

Key routine operative data will be captured on surgical approach, principal diagnosis and key steps of procedure. This will be taken from the routine recording on the NELA database and/or clinical notes.

### **At discharge:**

The complications experienced by the participant post-op up to discharge will be captured from clinical notes, and from consultation with the clinical team. The research team, in conjunction with the local PI will assign a Clavien Dindo classification to complications.

Process measures (time to line insertion) will be captured from clinical notes.

Nutrition outcomes will be captured from clinical records. Intended dosing of PN (total calorie requirement), and proportion of this administered, will be captured from clinical records.

The participant will undertake a 30 second sit to stand test. This should be performed on the day of discharge. However, when this is anticipated to occur over a weekend with no research staff available, this may occur up to two days prior to discharge. EQ-5D-5L, PRO-diGI, patient satisfaction visual analogue scale, and QoR-15 will be captured at this timepoint, with completion either directly by the patient or administered by a member of the research team. Barthel Index will be completed by a member of the research team. Discharge details will also include details of discharge destination (usual residence, residential, or nursing home).

### **Day 30 post-operation**

The participant will be contacted by the research team. Complications will be captured from medical records, and from telephone discussion with the participant to identify those complications managed in the community. This includes unplanned readmissions if the patient has been discharged post-operation. Patient reported outcomes of PRO-diGI, QoR-15, EQ-5D-5L, and patient treatment satisfaction will be collected using an adaptive approach of telephone or electronic administration. Barthel Index will be completed by a member of the research team. These assessments should take place at day 30 +/- 3 days post-operation.

## **Day 90 post-operation**

Complications will be captured from medical records, and from telephone discussion with the participant to identify complications managed in the community. This includes unplanned readmissions following discharge. Patient reported outcomes of PRO-diGI, QoR-15, and patient treatment satisfaction will be collected using an adaptive approach of telephone or electronic administration. Barthel Index will be completed by a member of the research team. These assessments should take place at day 90 +/- 7 days post-operation.

## 9.1 Schedule of assessments

Table 4: The timing of assessments is presented in the table below

| Activity                                      | Screening | Baseline | Surgery
(Day 0) | During
hospital stay
for index
surgery | At discharge | Day 30 ± 3
days | Day 90 ± 7
days |
|---|-----------|----------|--------------------|---|--------------|--------------------|--------------------|
| Eligibility check                             | ✓         |          |                    |   |              |                    |                    |
| Valid informed consent                        | ✓         |          |                    |   |              |                    |                    |
| Demographics (age, sex, ethnicity, diagnosis) |           | ✓        |                    |   |              |                    |                    |
| Relevant medical history taken                |           | ✓        |                    |   |              |                    |                    |
| NELA risk score                               |           | ✓        |                    |   |              |                    |                    |
| MUST score                                    |           | ✓        |                    |   |              |                    |                    |
| NRS-2002 score                                |           | ✓        |                    |   |              |                    |                    |
| Randomisation                                 |           | ✓        |                    |   |              |                    |                    |
| Contact Details                               |           | ✓        |                    |   |              |                    |                    |
| Routine Bloods                                |           | ✓        |                    |   |              |                    |                    |
| Surgery                                       |           |          | ✓                  |   |              |                    |                    |

| Activity  | Screening | Baseline | Surgery
(Day 0) | During
hospital stay
for index
surgery | At discharge | Day 30 ± 3
days post-op | Day 90 ± 7
days post-op |
|---|-----------|----------|--------------------|---|--------------|----------------------------|----------------------------|
| PICC/CVC Line insertion/removal   |           |          |                    | ✓   |              |                            |                            |
| Chest x-ray   |           |          |                    | ✓   |              |                            |                            |
| PN (including date of commencement)                                       |           |          |                    | ✓   |              |                            |                            |
| Use of nutritional interventions,
including type and frequency.        |           |          |                    | ✓   |              |                            |                            |
| Discharge details (destination and
length of stay)                     |           |          |                    |   | ✓            |                            |                            |
| Complications (including infectious
complications and mortality) - CCI |           |          |                    |   | ✓            | ✓                          | ✓                          |
| Unplanned readmissions  |           |          |                    |   |              | ✓                          | ✓                          |
| 30 second sit to stand  |           |          |                    |   | ✓            |                            |                            |
| Barthel Index   |           |          |                    |   | ✓            | ✓                          | ✓                          |
| Patient reported measures  |           |          |                    |   |              |                            |                            |
| EQ-5D-5L  |           | ✓        |                    |   | ✓            | ✓                          | ✓                          |
| PRO-diGI gastrointestinal recovery
measure                             |           |          |                    |   | ✓            | ✓                          | ✓                          |

| Activity  | Screening | Baseline | Surgery
(Day 0) | During
hospital stay
for index
surgery | At discharge | Day 30 ± 3
days | Day 90 ± 7
days |
|---|-----------|----------|--------------------|---|--------------|--------------------|--------------------|
| Quality of recovery (QoR-15)  |           |          |                    |   | ✓            | ✓                  | ✓                  |
| Assessment of patient treatment satisfaction Visual Analog Scale (VAS)            |           |          |                    |   |              | ✓                  | ✓                  |
| Health Resource Use Questionnaire Form  |           | ✓        |                    |   |              | ✓                  | ✓                  |
| Safety and complications   |           |          |                    |   |              |                    |                    |
| Side effects/adverse events   |           |          | ✓                  | ✓   | ✓            | ✓                  | ✓                  |
| Nutrition intervention related complications including metabolic and line-related |           |          | ✓                  | ✓   | ✓            | ✓                  | ✓                  |
| Process measures   |           |          |                    |   |              |                    |                    |
| Use and duration of PN/ other nutritional interventions                           |           |          |                    |   | ✓            | ✓                  | ✓                  |
| Time to line insertion & time to commence PN                                      |           |          |                    | ✓   |              |                    |                    |

## 9.2 Withdrawal and changes in levels of participation

Informed consent is defined as the process of learning the key facts about a clinical trial before deciding whether or not to participate. It is a continuous and dynamic process and participants should be asked about their ongoing willingness to continue participation at all visits. Participants should be aware from the beginning that they can freely withdraw (cease to participate) from the trial at any time. A participant may wish to cease to participate in a *particular* aspect of the trial.

Participants found to be ineligible post randomisation should be followed up according to all trial processes and will still have their data analysed unless they explicitly change their level of participation.

The changes in levels of participation within the trial are categorised in the following ways:

**No trial intervention:** The participant would no longer like to receive the trial intervention, but is willing to be followed up in accordance with the schedule of assessments and if applicable using any central UK NHS bodies for long-term outcomes (i.e., the participant has agreed that data can be collected and used in the trial analysis).

**No trial related follow-up:** The participant does not wish to attend trial visits in accordance with the schedule of assessments, but is willing to be followed up at standard clinic visits and if applicable using any central UK NHS bodies for long-term outcomes (i.e., the participant has agreed that data can be collected at standard clinic visits and used in the trial analysis, including data collected as part of long-term outcomes).

**No further data collection:** The participant is not willing to be followed up in any way for the purposes of the trial AND does not wish for any further data to be collected (i.e., only data collected prior to any changes of levels in participation can be used in the trial analysis).

The details of changes of levels in participation within trial (date, reason and category of status change) should be clearly documented in the source documents.

If a participant loses capacity during the study, data previously collected will be retained. Ongoing collection of patient reported outcome measures (PROMs) will not be carried out, but information from hospital documentation of unplanned readmission, complications, and mortality, will be collected and used in the analysis if the participants Personal Consultee

(England/Wales)/Legal Representative (Scotland) has provided a declaration/consent that the participant should remain in the study.

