### **5.3 Patients unable to provide informed consent (England and Wales)**

Some patients who are eligible for the trial will have a temporary impairment to their ability to provide consent. This impairment will result from the condition for which they require surgical intervention. Patients who have a long-term cognitive impairment that prevents fully informed consent will be excluded from the trial.

If the patient does not have capacity for fully informed consent due to temporary impairment, where possible the trial will be briefly discussed with them, and they will be given the Summary PIS. In accordance with guidelines from the Health Research Authority (HRA), the trial will also be

discussed with the patient's relative or carer (Personal Consultee). The Personal Consultee will be asked if the patient has expressed any prior wishes with regard to participating in research and if the patient has expressed a preference, then this will be adhered to. The relative is not asked to provide consent on behalf of the patient but rather provide an opinion on the views and feelings of the potential participant.

The patient's relative/carer (Personal Consultee) must be:

- Told that they are being asked to advise on the views and feelings they believe the adult would have towards participation in the study
- Told that they are free to decide whether they wish to provide this advice or not
- Given sufficient information, in an understandable form, about the study to ensure that they provide informed advice

A Consultee Information Sheet will be provided to facilitate the assent process. If the consultee agrees that the patient can be included in the trial, the consultee will initial, sign and date the latest version of the Consultee Declaration Form.

If no Personal Consultee is available, the patient will not be included in the trial.

It is imperative that when a Personal Consultee has been consulted, that as soon as the participant is able to provide informed consent, the trial is explained to them and their written informed consent is sought. The participant will be given the PIS for delayed consent and their consent will be documented through the initialling, signing and dating of the latest version of the ICF for delayed consent.

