If, at any stage, the participant refuses consent for involvement in the trial or asks to be withdrawn from the trial, their wishes must be adhered to. If the participant does not wish to continue, they will be withdrawn from the trial. Any data collected up to the point of withdrawal will be retained and used in the trial.

For a small number of patients (<2%), it is anticipated that they will not regain consciousness/capacity within 30 days, as these patients will have already received the intervention and reached the primary outcome, their data will be retained for use in the final analysis. If these patients regain capacity after 30 days, where practical, the local research team will consent them for their involvement in the study. In the event that the patient never regains capacity or dies, then they will remain in the trial and their data will be included in the analysis.

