## **5.5 Ongoing consent**

At each visit, the participant's willingness to continue in the trial will be ascertained (through the participant, personal consultee or legal representative as appropriate) and documented in the medical notes. Throughout the trial, the participant, personal consultee or legal representative will have the opportunity to ask questions about the trial. Any new information that may be relevant to the participant's continued participation will be provided. Where new information becomes available which may affect the participants' decision to continue, participant, personal consultee or legal representative will be given time to consider this information and if happy to continue they will be re-consented. Re-consent will be documented in the medical notes. The participant's right to withdraw from the trial will remain.

In the UK, if a participant loses capacity during the 90 day study period, the advice/consent of a Personal Consultee (England/Wales)/Legal Representative (Scotland) on whether the participant should remain in the study will be sought and a declaration/consent obtained as described in sections 5.3 and 5.4.

Electronic copies of the PIS and ICF will be available from the Trial Office and will be printed or photocopied onto the headed paper of the local institution.

With the participant's consent (or assent from personal consultee/legal representative), their General Practitioner (GP) will also be informed that they are taking part in the trial.

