### 15.1 Within-trial economic evaluation

This will adopt recommended methods for economic evaluations that are undertaken alongside controlled trials. Resource use will cover length and type of hospital stay (as described by healthcare resource group); which will include adverse events (e.g. infections and further operations) but not details of PN. Days of PN will be recorded separately, for the purposes of the trial. After discharge, all other NHS and personal social service utilisation will be collected using a patient questionnaire, together with private expenditure and time off work for an analysis from a societal perspective. Unit costs will use mean national reference cost values, whilst the costs of PN will be based on a survey of consumable costs in the trial hospitals and estimates of staff time required for the initiation and cessation of PN. QALYs will be calculated based on EQ-5D-5L recorded at baseline, discharge, 30 days and 90 days. Utilities will be calculated using the method recommended by NICE at the time of analysis; whilst NICE currently recommends the use of a mapping approach, it is anticipated that an official tariff will be available in the near future. An incremental analysis will then be undertaken. A comprehensive one-way sensitivity analysis will be undertaken, together with a probabilistic sensitivity analysis with plots on the cost-effectiveness plane and the generation of cost-effectiveness curves and its associated frontier.

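### Section 9.2 stops PROMs after any loss of capacity with no restart on recovery, and does not line up with Section 5.5

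*Protocol*

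**What the plan says.** Protocol Section 9.2 sets the rule for capacity lost after enrolment. It opens: "If a participant loses capacity during the study, data previously collected will be retained". It goes on: "Ongoing collection of patient reported outcome measures (PROMs) will not be carried out, but information from hospital documentation of unplanned readmission, complications, and mortality" is still gathered and analysed, provided the consultee or legal representative "has provided a declaration/consent that the participant should remain in the study". Neither the length of the incapacity nor its reversal is mentioned.

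Section 5.5 covers the same event: "if a participant loses capacity during the 90 day study period, the advice/consent of a Personal Consultee" (or the Scottish legal representative) is sought on whether the participant stays in, following Sections 5.3 and 5.4. It places no limit on which outcomes are collected. Section 5.3, with matching text in 5.4, requires that once someone has been consulted on a participant's behalf, "as soon as the participant is able to provide informed consent, the trial is explained to them and their written informed consent is sought". Neither section mentions PROMs.

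The outcomes at issue are these:

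- Table 14 lists five participant-completed questionnaires: EQ-5D-5L, PRO-diGI, QoR-15, health resource use and satisfaction. Table 4 puts all five under patient-reported measures.
- Section 15.1 states: "QALYs will be calculated based on EQ-5D-5L recorded at baseline, discharge, 30 days and 90 days". It takes NHS and social care use after discharge from a patient questionnaire.
- The Barthel index is staff-rated. Section 8.2.2.1 gives it as: "Barthel index of function (including activities of daily living)[40], completed by the clinical team / site staff at discharge, 30 and 90 days post-operation".
- Table 7 lists delirium and unplanned ICU admission as expected events for all participants.

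**The concern.** In this population, loss of capacity after surgery will often be temporary. Section 5 itself attributes temporary incapacity to critical illness, pain, anxiety and opiates. A rule triggered by any such episode, with no way back, discards day-30 and day-90 questionnaires that a recovered participant could complete by telephone or electronically.

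These losses would not fall at random. The trigger is a post-operative event of the kind the CCI counts, so the missing PROMs would come mainly from participants with complications. The cost-effectiveness analysis over 90 days is the primary economic objective (Section 2.2.2). It needs both EQ-5D-5L and patient-reported resource use, and no proxy completion is described. The SAP can specify a model for missing values, but it cannot recover data that sites were told not to collect.

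A second, smaller problem is that Section 9.2 names three kinds of data that continue and is silent on the rest. A site could reasonably be unsure what else to record.

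**Working it through.** **1. Two rules for one event.** Take a participant who consents, has a short delirium with loss of capacity before discharge, and recovers.

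| Question | Section 9.2 | Section 5.5 (through 5.3/5.4) |
|---|---|---|
| Who agrees to continued participation? | Consultee or legal representative | Consultee or legal representative |
| Which outcomes continue? | Readmission, complications and mortality named; PROMs stopped | No restriction |
| What happens on recovery? | Not addressed | Participant's own consent sought; PROMs not mentioned |

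The cross-reference in 5.5 makes re-consent the natural reading, but it does not override the explicit stop in 9.2.

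**2. What a literal reading removes.** If capacity is lost before discharge:

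- EQ-5D-5L is scheduled at baseline, discharge, day 30 and day 90. Three of the four points are lost, which is every post-operative utility.
- QoR-15 and PRO-diGI are scheduled at discharge, day 30 and day 90. All are lost.
- Satisfaction at days 30 and 90 is lost, as are the two follow-up resource-use forms (Table 4).

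Data collected before the loss are kept and deaths are still recorded. The QALY is therefore partly missing, and the participant remains in the trial.

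**3. Whether the loss is avoidable.** The only capacity figure is in Section 5.3 (repeated in 5.4): "For a small number of patients (<2%), it is anticipated that they will not regain consciousness/capacity within 30 days". It concerns people enrolled without capacity, so it is not a rate of later loss. It does show that the protocol expects most incapacity of that kind to resolve by the day-30 contact.

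**4. Primary outcome.** The planned sample size reproduces from SD 27, difference 6, two-sided 5% and 90% power: n per arm = 2 × (1.960 + 1.282)² × 27² / 6² ≈ 425.6, rounded up to 426. Then 426 / 0.95 = 448.4, rounded up to 449 per arm, or 898 in total. Complications and mortality are still collected under 9.2 with the declaration or consent, so neither the CCI nor this calculation changes.

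**5. Number at risk.** No frequency of later incapacity is given. On an assumed 5–20%:

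- 449 × 0.05 = 22.45, about 22 per arm
- 449 × 0.20 = 89.8, about 90 per arm

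These are participants with some PROMs at risk. The avoidable part is smaller, because some will die or not regain capacity.

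**6. Effect on the treatment comparison.** Suppose fractions p₁ (early PN) and p₀ (control) are affected, affected participants score D lower on average, and the effect δ is the same in everyone else. The full-population difference is then δ + (p₀ − p₁) × D, while a complete-case analysis estimates δ. The gap (p₀ − p₁) × D is zero if both arms lose capacity equally often. The protocol supplies neither the fractions nor D, so neither size nor direction can be given.

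**The case against.** The strongest reply is that ordinary practice resolves this. Section 5.5 leads to re-consent on recovery, willingness to continue is checked at each visit, and a sensible site would then hand over the questionnaires. Handling of missing secondary data is left to the SAP, and the primary outcome is safe. Delirium also need not mean incapacity at a scheduled assessment. All of this is fair, and it means permanent loss of PROMs is a literal reading of 9.2, not an established consequence. What remains is that 9.2 says in terms that collection will not happen, and nothing elsewhere tells a site to restart it.

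A reader might go further and infer that the Barthel index, length of stay, discharge destination, and PN use and calories also stop. The documents do not support that. Section 9.2 does not say that *only* its three items continue. The Barthel index is completed by staff and is absent from Table 14. Nutrition data come from clinical records (Section 9), stay and destination from hospital records (Section 8.2.2.1), and adherence from clinical notes (Section 7.9). The residual ambiguity is real but modest: Table 3 groups the Barthel index with the 90-day questionnaires, so a site could treat it as stopping with them.

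**Conclusion.** The point holds for PROMs and patient-reported resource use. Section 9.2 fixes a stop that is wider than it needs to be and is not reconciled with Section 5.5. Followed literally, it creates avoidable, complication-related missing data in the patient-reported secondary outcomes and in the primary 90-day cost per QALY. For staff-completed and record-based outcomes, the finding is unclear wording only.

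The size is unknown. About 22–90 of 449 per arm with some PROMs at risk rests wholly on the assumed 5–20% frequency. A reader might also infer that the rule hides a benefit of early PN. That would require PN to change how often capacity is lost, which the protocol does not claim: Section 1.2.4 anticipates effects on wound healing and infection, and delirium appears only as an expected event. The primary CCI is unaffected where the consultee or legal representative agrees.

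**What to change.** Amend Section 9.2 and cross-refer it to Section 5.5, stating that:

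- PROMs and participant-completed resource-use forms are paused while capacity is absent. They resume at the next scheduled time point once capacity returns and the participant agrees.
- With the consultee declaration or legal representative consent in place, all record-based and staff-completed outcomes continue. These include complications, readmission, mortality, the Barthel index, length of stay, discharge destination, and PN use and calories.

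The cost is a short protocol change and matching wording in the consultee and legal representative forms, with no new assessments. The small downside is that sites must re-check capacity at the day-30 and day-90 contacts.
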